6.3.2. Study Day -35

This visit may occur within a +/- 7 day window, relative to Study Day -63. The following procedures will be performed on Day -35:

- Blood pressure in the supine position after at least 3 minutes of rest;
- Serum creatinine for an eGFR calculation;
- First morning urinary protein and creatinine measurements for a PCR calculation;
- First morning urinary albumin, MCP-1, EGF, and microscopic RBC count for ACR, MCP-1:creatinine, EGF:MCP-1 ratio, and hematuria assessment;
- Recording of changes in concomitant medication;
- Recording of all adverse events;
- The subjects will be reminded to stay on a stable dose(s) or their RAAS blocker(s), and to come back to the study center for two back-to-back study visits in the Day -7 to -2 window.

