6.3.3. Study Day -7 to -2 Window

Two back-to-back study visits will occur within the Study Day -7 to -2 window, relative to Study Day -63. The following procedures will be performed on these two study days:

- Blood pressure in the supine position after at least 3 minutes of rest (on both days);
- Serum pregnancy test for women of child-bearing potential (on the first of the two days);

- Serum creatinine for an eGFR calculation (on the first of the two days);
- First morning urinary protein and creatinine measurements for a PCR calculation (on both days);
- First morning urinary albumin, MCP-1, EGF, and microscopic RBC count for ACR, MCP-1:creatinine, EGF:MCP-1 ratio, and hematuria assessment (on the first of the two days);
- Recording of changes in concomitant medication;
- Recording of all adverse events;
- If the subject is still eligible for study continuation, i.e.:
 - If the geometric mean of the two first morning urinary PCR levels is still $> 1 \text{ g/g}$ creatinine but $\leq 8 \text{ g/g}$ creatinine,
 - If the subject's eGFR has not deteriorated $> 10 \text{ mL/min/1.73 m}^2$ over the prior 8-week run-in period,

the subject will come for their Study Day 1 visit. The subjects will be reminded to stay on a stable dose(s) or their RAAS blocker(s). If a subject is not eligible at this stage, the subject will be discontinued from study.

6.4. Study Day 1

If eligible for continuation in the study, the subject will visit the study center on Day 1 for the following procedures:

- A physical examination (excluding genitourinary, ophthalmic, and female breast assessments); body weight assessment will be performed;
- Vital signs (temperature, blood pressure, heart rate) will be measured supine after at least 3 minutes of rest;
- Serum chemistry and hematology; an eGFR will be calculated based on MDRD equation;
- Urinalysis, including pH, specific gravity, glucose, nitrite, ketones, bilirubin, urobilinogen, RBCs, and WBCs on a first morning urine sample collection;
- Urinary protein, creatinine, albumin, MCP-1, EGF, and microscopic RBC count on a first morning urine sample collection;
- Serum IgA and plasma C3 measurement;
- A plasma sample will be collected for baseline PD marker and PK measurement;
- A urine sample will be collected for PD marker assessment;
- Any changes in concomitant medication use will be recorded;

Note that the above listed procedures must be performed prior to taking study medication.

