6. DEFINITIONS

Table 1. Terminology and Definition

Terminology	Definition
Age	Age is calculated as the number of full years since date of birth at the time of signing the Informed Consent Form (ICF).
Study Drug	CCX168
Study Day	The number of days relative to the very first day when the subject receives a dose of the study drug. For visits prior to the first dose of the study drug, Study Day is calculated as Visit Date minus the first dose date. For visits after the first dose, Study Day is calculated as Visit Date minus the first dose date plus 1.
Screened	Subject who has signed informed consent.
Enrolled	Subject who has entered the RAAS dose titration/run-in period
Treated	Subject who has received a dose of the study drug.
Treatment Period	From the first dose to the last dose, inclusive, of the study drug
Follow-up Period	After the last dose, exclusive, of the study drug
Completer for the treatment	Subject who has completed the 12 weeks of the treatment period with Day 85 assessment.
Completer for the study	Subject who has completed the 12 weeks of the treatment period and follow-up period.
Baseline	Generally, baseline is defined as the non-missing value collected most recent to and before the time of the very first dose of the study drug unless specified otherwise. For urinary PCR, baseline will be the geometric mean of the two measurements made in the Day -7 to -2 window plus the Day 1 (pre-dose) value. For the eGFR, urinary ACR, MCP-1:creatinine ratio, EGF:MCP-1 ratio, and microscopic RBC count, baseline will be the geometric mean of the one measurement made in the Day -7 to 2 window plus the Day 1 (pre-dose) value.
Pre-treatment Adverse Event	Adverse event starting/worsening prior to the time of the first dose of the study drug administration.
Treatment Emergent Adverse Event	Adverse event starting/worsening between the first and last dose of the study drug administration.
Post-treatment Adverse Event	Adverse event starting/worsening after the last dose of the study drug.
Prior Medication	Medication on the Prior/Concomitant Medication CRF with start date prior to Study Day 1.
Concomitant Medication	Medication collected on the Prior/Concomitant Medication CRF with end date on/after Study Day 1, including missing end date or medication ongoing.

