10. STATISTICAL METHODS

10.1. Sample Size Justification

The sample size for the study is based on the slope of the urinary ACR observed in a study in patients with ANCA-associated vasculitis while receiving CCX168. The mean slope was -1.32, with a standard deviation of 1.67 over 12 weeks, and -4.62, with a standard deviation of 4.77 over the initial 4 weeks of the treatment with CCX168 in ANCA-associated vasculitis. Assuming a mean difference in pre-treatment and on-treatment slopes of 4.6, a sample size of 15 subjects will provide approximately 80% power and 20 subjects approximately 90% power to detect a difference in slopes.

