10.7. Efficacy Evaluation

10.7.1. Change in slope of first morning urinary PCR (protein:creatinine ratio) from the 8-week RAAS blocker run-in period to the 12-week treatment period

Slope will be calculated for each subject using the time points as follows.

Time Window for Slope Calculation	Time Points Used for Slope Calculation	Corresponding Time Value Used for Regression*
Weeks -8 to -5	Day -63 and Day -35	-63 and -35
Weeks -4 to -1	Day -35, Day -7 to 02, and Day 1	-35, -5, and 0
Weeks -8 to -1	Day -63, Day -35, Day -7 to 02, and Day 1	-63, -35, -5, and 0
Weeks 1 to 4	Day 1, Day 8, Day 15, and Day 29	0, 7, 14, 28
Weeks 1 to 12	Day 1, Day 8, Day 15, Day 29, Day 57, and Day 85	0, 7, 14, 28, 56, and 85

* For Time Point Day -7 to -2, time value of -5 will be used. For Study Day on/after the first dose, one day is subtracted to return the value to continuous scale such that Day 0 is day of first dose.

For the primary efficacy endpoint analysis, the slope of the urinary PCR during the 8-week run-in period, during the initial 4-week treatment period, as well as the full 12-week treatment period will be calculated for each subject. The mean slope for the 8-week run-in period will be compared to the mean slope for the initial 4-week, as well as the full 12-week treatment period to evaluate the treatment effect of CCX168.

If the slope for the first 4 weeks of the run-in period is steeper than the slope of the last 4 weeks of the run-in period, indicating that steady state has not been achieved over the first 4 weeks, the slope of the last 4 weeks of the run-in period will be used as the baseline slope, instead of the slope over the 8 weeks of the run-in period. This comparison will be performed by the paired t-test. The 95% confidence interval for the difference in the mean slopes will be presented.

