10.7.4. Change in slope from the run-in period to the treatment period for

- a. urinary ACR,
- b. eGFR,
- c. urinary MCP-1:creatinine,
- d. urinary EGF:MCP-1, and
- e. urinary microscopic RBC counts

These variables will be summarized similarly to the primary efficacy variable.

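### In SAP 10.7.1 the Weeks 1 to 12 slope codes Day 85 as 85, but the SAP's own rule gives 84; the 12-week slope comes out about 1% off

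*SAP*

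**What the plan says.** SAP 10.7.1 defines the per-subject slopes through a table of visits and fixed regression times. The Weeks 1 to 12 row uses the visits on Days 1, 8, 15, 29, 57 and 85 and gives them the times "0, 7, 14, 28, 56, and 85". The footnote to the table states the conversion for days on or after the first dose: "one day is subtracted to return the value to continuous scale such that Day 0 is day of first dose".

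The Study Day definition in SAP section 6 says the same from the other side: "For visits after the first dose, Study Day is calculated as Visit Date minus the first dose date plus 1". Protocol section 3 sets a treatment period of 84 days.

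The Weeks 1 to 12 slope is the on-treatment part of the primary efficacy endpoint. SAP 10.7.4 carries the method over to urinary ACR, eGFR, MCP-1:creatinine, EGF:MCP-1 and microscopic RBC count: "These variables will be summarized similarly to the primary efficacy variable".

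**The concern.** The row and its footnote cannot both be followed. A programmer who copies the printed times and a validator who applies the footnote would each comply with the SAP and would report different 12-week slopes. Protocol 7.10 gives the SAP precedence over the protocol's statistical methods section, so the protocol's description does not settle the matter.

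The discrepancy touches only one side of the paired comparison. The run-in slopes use Days -63, -35, the Day -7 to -2 point and Day 1, which are coded consistently, so the error does not cancel in the difference between treatment slope and run-in slope. What is at stake is the accuracy of the reported primary estimate and its interval, and whether the result can be reproduced from the SAP.

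**Working it through.** **1. Apply the SAP's rule (time = Study Day - 1).**

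| Study Day | 1 | 8 | 15 | 29 | 57 | 85 |
|---|---|---|---|---|---|---|
| By the rule | 0 | 7 | 14 | 28 | 56 | 84 |
| As printed | 0 | 7 | 14 | 28 | 56 | 85 |

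Five of the six printed values reproduce; the last does not. The Weeks 1 to 4 row (0, 7, 14, 28) also follows the rule. Pre-dose Study Days are visit date minus first-dose date with nothing added, so -63 and -35 need no shift.

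**2. Effect on the least-squares slope.** Each subject's slope is the sum of w_i y_i, with w_i = (t_i - mean t)/Sxx.

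- Printed times: sum 190, mean 31.667, sum of squares 11390, Sxx = 11390 - 190²/6 = 5373.3.
- Corrected times: sum 189, mean 31.5, sum of squares 11221, Sxx = 11221 - 189²/6 = 5267.5.

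Ratio of the weights, printed over corrected:

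| Day 1 | Day 8 | Day 15 | Day 29 | Day 57 | Day 85 |
|---|---|---|---|---|---|
| 0.985 | 0.987 | 0.990 | 1.027 | 0.974 | 0.996 |

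**3. Average slope for several true courses** (true times 0 to 84, fitted with the printed times):

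- Linear: the factor is the cross-product of the two sets of centred times over the printed Sxx, 5320.0/5373.3 = 0.990. A true slope of -0.01000 per day is reported as -0.00990.
- Exponential fall exp(-t/k), with k = 7, 14, 28, 56 days (assumed): 1.39%, 1.31%, 1.21%, 1.11% flatter.
- Drop seen only at Day 85: 0.4% flatter.
- Step after Day 1, then constant: 1.5% flatter.

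**4. Spread.** The standard deviation of a slope due to independent measurement noise is proportional to 1/sqrt(Sxx), so its factor is sqrt(5267.5/5373.3) = 0.990. Between-subject variation in a linear slope is multiplied by the same 0.990 as the mean.

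**5. Scale, for illustration only.** SAP 10.1 quotes ACR slopes from another disease: "The mean slope was -1.32, with a standard deviation of 1.67 over 12 weeks". Multiplying by 0.990 gives a mean of -1.307 and a standard deviation of 1.653.

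**6. The paired difference.** Let the mean run-in slope be a fraction f of the true treatment slope b. For a linear course the mean difference moves from (1 - f)b to (0.990 - f)b. Relative to the true difference, the loss is 0.0099/(1 - f): 1.0% for f = 0, 1.3% for f = 0.25 and 2.0% for f = 0.5.

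The standard deviation of the difference also falls. The ratio of mean to standard deviation, which drives the t statistic, changes by a factor of 0.994 to 0.9998 for a flat run-in and 0.984 to 0.996 for f between 0.25 and 0.5. These factors rest on assumed inputs: log-scale noise standard deviation 0.1 to 0.3, treatment slope -0.003 to -0.01 per day, between-subject coefficient of variation 0.5 to 1.265, run-in slope standard deviation 0 to 1 times that of the treatment slope, and a Day 1 sample shared by both slopes. The SAP does not say that PCR is log-transformed for the slopes, so the factors show order of magnitude only.

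**The case against.** The strongest reply is that this is a single-digit slip in an SAP that calls itself version 0.2, in a table that also misprints the end of the Day -7 to -2 window in two rows. The rule stands directly beneath the table, so the intended value can be recovered, and an effect of about 1% in a pilot of up to about 20 subjects changes nothing that matters. The part about size stands, and it is why the point is minor. It does not remove the inconsistency: the table gives the explicit time values for the regression, and a program built from it would use 85.

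The Day 85 visit window does not explain the entry. Days 29 and 57 have the same window of plus or minus 2 days and are coded 28 and 56.

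A reader might infer three stronger things, none of which the documents support:

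- **That the primary test is compromised.** It is not. Mean and standard deviation shrink together, and the t statistic hardly moves.
- **That the error always works against the drug.** The pull is toward a zero slope on average, which is not the same as toward a zero treatment effect; the effect on the difference depends on the run-in slope. Nor does every subject's slope shrink, because the Day 29 weight rises by 2.7% while the other five fall by 0.4 to 2.6%.
- **That fixed nominal times are themselves an error, since visits have windows.** The SAP states its convention openly: "For Time Point Day -7 to -2, time value of -5 will be used", and SAP 10.2.11 summarizes data by the recorded visit without visit windows. Regressing on actual dates would be a preference against that convention, not the correction of a mistake.

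**Conclusion.** The entry for Day 85 is wrong as written, and this follows from the SAP alone: the footnote and the Study Day definition both give 84. The size is small. The 12-week slope is multiplied by 0.990 for a linear course, is about 1.1 to 1.4% flatter for exponential falls, and is 0.4% or 1.5% flatter for the two extreme shapes. The same factors apply to the primary PCR slope and the five secondary slopes. The run-in and Weeks 1 to 4 slopes are correct.

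The percentages assume visits on their nominal days and an ordinary least-squares line per subject. The statement that the paired t-test is essentially unchanged rests on the exact 0.990 factors for mean and spread of the 12-week slope and, for the paired difference, on the assumed ranges given with that calculation. The defect is in the reported slope, difference and confidence interval, not in the study's conclusion.

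**What to change.** In the Weeks 1 to 12 row of the SAP 10.7.1 table, change 85 to 84, so that the row reads 0, 7, 14, 28, 56 and 84. Make the same change in the program, and confirm that the primary PCR slope and the five slopes under SAP 10.7.4 all use it.

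The cost is one digit in the SAP and the matching value in the code. No data collection, visit, endpoint or sample size is affected.

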7.1. Primary Efficacy Endpoint

- Change in slope of first morning urinary PCR (protein:creatinine ratio) from the 8-week RAAS blocker run-in period to the 12-week treatment period.

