10.2. General Statistical Methods and Data Handling

10.2.1. General Methods

Unless specified otherwise, all summary tables will be presented by visit from baseline to end of study (Day 169).

Summary statistics will be presented, as well as 2-sided 95% confidence intervals on selected parameters, as described in the sections below. All data will be included in the subject data listing.

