10.2.7. Multiple Comparisons/Multiplicity

Not applicable.

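### The primary analysis compares the run-in slope with two treatment windows without saying which decides; if either may count, the chance of a false positive is about 8–9%

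*SAP*

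**What the plan says.** SAP 7.1 defines one primary efficacy endpoint: "Change in slope of first morning urinary PCR (protein:creatinine ratio) from the 8-week RAAS blocker run-in period to the 12-week treatment period". The heading of SAP 10.7.1 and Protocol 7.8 agree.

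The analysis text under that heading is wider. It introduces the primary analysis and then states that the mean run-in slope "will be compared to the mean slope for the initial 4-week, as well as the full 12-week treatment period", in order to evaluate the effect of CCX168. Protocol 7.10.4 and the synopsis say the same. On the test and the interval, SAP 10.7.1 says "This comparison will be performed by the paired t-test" and "The 95% confidence interval for the difference in the mean slopes will be presented". None of these places ranks the windows, calls one supportive, or states an alpha or a success rule. The only indication of level is SAP 10.2.1, which plans "2-sided 95% confidence intervals on selected parameters".

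SAP section "10.2.7. Multiple Comparisons/Multiplicity" is marked as not applying. In Appendix A, each population has one PCR slope table whose title names no window, and figures 2.1a and 2.1b show weeks 1 to 4 beside weeks 1 to 12.

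SAP 10.1 sizes the trial as follows: "Assuming a mean difference in pre-treatment and on-treatment slopes of 4.6", 15 subjects give about 80% power and 20 give about 90%. The slopes it cites from the vasculitis study are for urinary ACR: -1.32 (SD 1.67) over 12 weeks and -4.62 (SD 4.77) over the first 4 weeks.

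**The concern.** The endpoint points to 12 weeks, the sample size points to 4 weeks, and the analysis paragraph gives both equal standing. With no deciding contrast named, the 4-week result is available as a fallback if the 12-week result misses, and the plan does not exclude presenting it as the primary finding. Two chances at the nominal level then replace one. In an open-label, single-arm trial of about 20 subjects, there is no control group to temper such a reading.

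**Working it through.** **1. Reproducing the stated power.** A paired t-test has n-1 degrees of freedom and noncentrality difference × √n / SD of the paired difference. The documents do not give that SD. With equal SDs and zero correlation between the two slopes, it is √2 × 4.77 = 6.746.

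- Noncentrality: 4.6 × √15 / 6.746 = 2.641, and 4.6 × √20 / 6.746 = 3.050.
- One-sided 5% (critical t 1.761 and 1.729): power 80.7% and 90.2%, which matches the stated 80% and 90%.
- Two-sided 5% (critical t 2.145 and 2.093): power 69.0% and 82.4%, which does not.

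So with the stated difference of 4.6 and this SD, the stated power corresponds to one-sided 5%.

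**2. Correlation of the two contrasts.** The documents do not give it, but the SAP 10.7.1 time points determine it once an error structure is assumed. The time values are -63, -35, -5, 0 (run-in), 0, 7, 14, 28 (4 weeks) and 0, 7, 14, 28, 56, 85 (12 weeks). The last value is used as printed; the table's own footnote implies 84, and the difference is negligible.

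Take independent errors of unit variance. The sums of squares of time about the mean are 2566.75, 428.75 and 5373.33. Day 1 enters all three slopes, with weights 0.010032, -0.028571 and -0.005893.

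- Variance of 4-week minus run-in: 1/428.75 + 1/2566.75 + 2 × 0.010032 × 0.028571 = 0.003295.
- Variance of 12-week minus run-in: 1/5373.33 + 1/2566.75 + 2 × 0.010032 × 0.005893 = 0.000694.
- Covariance: 1/5373.33 + 1/2566.75 + 0.010032 × (0.028571 + 0.005893) = 0.000921.
- Correlation: 0.000921 / √(0.003295 × 0.000694) = 0.61.

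Other error structures (autoregressive, random walk, random slopes) give up to 0.71. With the last-4-week run-in slope as baseline, the range is 0.76–0.80.

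**3. Chance of at least one false positive.** Independent tests set the ceiling: 1 - 0.95² = 9.75%. Simulated paired t-tests with no effect (400,000 trials per cell) give:

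| Correlation | Two-sided 5% each, n=15 / n=20 | One-sided 5% each, n=15 / n=20 |
|---|---|---|
| 0.60 | 8.9% / 8.8% | 8.6% / 8.6% |
| 0.70 | 8.4% / 8.4% | 8.2% / 8.1% |
| 0.80 | 8.0% / 8.0% | 7.6% / 7.6% |

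On the two-sided basis about half of the error is false harm. The chance of falsely showing benefit in at least one window is 3.9–4.5%. On the one-sided basis the whole figure is false benefit. The 12-week test alone gives about 5% two-sided.

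**4. Power of the 12-week test.** With a difference of 1.32 and an SD of √2 × 1.67 = 2.362, noncentrality is 2.165 (n=15) and 2.500 (n=20).

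- One-sided 5%: 66% and 78%.
- Two-sided 5%: 52% and 66%.

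The result depends heavily on the missing SD. If the SD of the paired difference were 1.67 itself (a correlation of 0.5 between the two slopes), two-sided power would be 81.2% and 91.8%.

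**The case against.** The strongest reply is that the endpoint is defined once, consistently, as the 12-week contrast. Nothing in either document says that a positive 4-week result counts as success, so the either-window error belongs to a decision rule the plan never adopts. The study also calls itself a pilot, states no alpha, and plans mainly summaries and intervals. Formal error control is not normally expected in that setting.

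Much of this stands. A reader might infer that the plan's false-positive rate is 8–9% in place of 5%, or that a result in either window would be offered as proof of effect at 5%. The documents support neither. The first needs a success rule that is not written, and the second needs a confirmatory claim that is not made. On a two-sided basis, false benefit in at least one window is itself below 5%.

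What does not stand is the idea that the text already settles the matter. The plan names a hypothesis test, claims power for it, places both windows in the primary analysis, and takes its assumed difference from the window that the endpoint does not name. It neither permits nor rules out a 4-week claim.

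**Conclusion.** The concern holds as an ambiguity with a conditional cost. The primary analysis contains two comparisons of unstated rank and no multiplicity rule. The cost is an either-window error of about 8–9% at two-sided 5% per test if a 4-week result may be claimed as primary success, and none if the 12-week contrast alone decides.

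The figures rest on three assumptions:

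- a 5% level inferred from the 95% intervals;
- a correlation derived from the visit schedule, though the result changes little over 0.6–0.8;
- a fixed 8-week run-in baseline slope.

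The last assumption matters. SAP 10.7.1 also replaces the baseline slope with that of the last 4 run-in weeks when the first 4 are steeper, without saying whether this is decided per subject or on the group mean. In simulation with the rule applied per subject (steeper read as more negative), the false-positive rate of the 12-week contrast alone was 12–36%. Applied to the group mean, the either-window rate stayed at about 8–9%. This is a separate threat to the 5% level.

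It would also go too far to conclude that the trial is undersized for 12 weeks. The stated power, as written, uses a difference that is not the 12-week one, but the SD needed to judge the 12-week test is not given.

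**What to change.** In SAP 10.7.1 and 10.2.7, state that run-in versus the full 12 weeks is the single primary test, and give its alpha and sidedness. Label the 4-week comparison supportive, reported as an estimate with its confidence interval and no claim of success. Mark the deciding window in the PCR slope tables.

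In SAP 10.1, restate the power for the 12-week contrast, with the SD of the paired difference and the sidedness written out.

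The change is to wording only and needs no extra subjects. The sponsor gives up a claim on the 4-week window, and the restated power may be well below 80% and 90%, depending on the SD.

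If the sponsor wants both windows to count, 2.5% per test holds the joint error at about 4.1–4.6%. On the 4-week inputs, power then falls from 80.7% and 90.2% to 69.0% and 82.4% (one-sided), or from 69.0% and 82.4% to 56.4% and 72.7% (two-sided), at n=15 and n=20.

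Naming one test does not by itself secure 5%. The baseline-slope replacement rule needs its own correction.

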8. ANALYSIS POPULATIONS

The following subject populations will be evaluated and used for presentation and analysis of the data:

- **Safety Population** includes of all subjects who have received at least one dose of study drug.

- **Modified Intent-to-Treatment (mITT) Population** includes all subjects who have received at least one dose of study drug, and have at least one post baseline urinary PCR assessment.
- **Per-Protocol (pP) Population** includes all mITT subjects who have complied with the protocol for the study drug administration, have been on stable RAAS dose, and not taken protocol-prohibited concomitant medications.

The Safety population will be used for the summaries of disposition, demographics, baseline characteristics, medical history, and prior/concomitant medications. Additionally, the Safety population will be used for the summaries of adverse events, laboratory tests, ECG, and vital signs.

The mITT and pP populations will be used for the summaries of the efficacy endpoints.

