9.2. Protocol Deviations

All protocol deviations will be classified as major or minor based on the following guidelines:

- Major protocol deviations are those that violate Good Clinical Practice (GCP) guidelines (ICH E6) and impact the ability to analyze the data collected. Examples may include but are not limited to: failure to administer the informed consent prior to initiating study procedures; non-compliance with taking study medication (less than 75% of medication taken based on study records or low plasma CCX168 concentrations indicating non-compliance); violations of inclusion and/or exclusion criteria that could affect the efficacy results.
- Minor deviations may include but are not limited to: out-of-window visits; scheduled assessments omitted or performed in improper sequence.

Protocol deviations will be categorized for data summary purpose.

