10.2.9. Withdrawals, Dropouts, Loss to Follow-up

Subjects who withdrew from the study will be included in the data listing and summary tables where applicable.

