10.2.10. Missing, Unused, and Spurious Data

No imputation will be carried out for missing data points.

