10.4. Subject Disposition

The number of subjects who have signed the informed consent, who entered the titration period, who entered the run-in period, who received study drug, who completed the 12-week treatment period of the study, who discontinued the 12-week period early (with reasons for discontinuation), who completed the

12-week follow-up period, who discontinued the 12-week follow-up period early (with reasons for discontinuation), will be tabulated.

A by-subject data listing of study completion information, including the reason for premature study withdrawal, if applicable, will be presented. If discontinuation is due to an AE, the AE will be specified.

Major and minor protocol deviations will be included in the subject data listing. Subjects with major protocol deviations affecting efficacy evaluation will be excluded from the pP population.

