10.7.2. Proportion of subjects achieving renal response

Renal response is defined as (1) a decrease in proteinuria from baseline to Day 85 to a level of <300 mg/g creatinine and (2) maintaining the Day 85 estimated glomerular filtration rate (eGFR) within 15% of baseline. The number (%) of subjects achieving renal response will be calculated and presented. Subjects who discontinued prior to Week 12 will be counted as non-responders.

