10.8.1. Drug Exposure

Study drug compliance will be calculated for each patient by dividing the total number of capsules taken (number dispensed – number returned) by the total number prescribed. Duration of subject on CCX168 will be calculated as the time interval (weeks) between first and last dose of the study drug, inclusive. The total number of capsules prescribed is calculated as 6 capsules/day x number of days in the duration. The % compliance and duration of exposure will be summarized with descriptive statistics.

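### The primary PCR slopes are fitted at nominal times that are wrong for Day 85, loose for Day -35 and unclear for Early Termination samples; secondarily, a short series counts as much as a full one

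*SAP*

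**What the plan says.** SAP 10.7.1 tabulates the visits and regression times for each slope. The 12-week treatment slope uses 0, 7, 14, 28, 56 and 85. The 8-week run-in slope uses -63, -35, -5 and 0. The footnote says that study days from first dose onward are reduced by one, so that first dose is time 0. If the first-4-week run-in slope is steeper than the last-4-week one, the last-4-week slope becomes the baseline. Then: "This comparison will be performed by the paired t-test".

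Protocol 6.3.2 gives the Day -35 visit a window of 7 days either way. Protocol 4.4 and 7.4 ask subjects who withdraw before Day 85 to have the Day 85 procedures, recorded as an Early Termination visit. The slope table has no such visit, and SAP 10.2.11 assigns data by eCRF visit label without windows.

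On incomplete series, the mITT population (SAP 8) asks only that treated subjects "have at least one post baseline urinary PCR assessment". SAP 10.2.10 adds "No imputation will be carried out for missing data points", and SAP 10.2.9 says "Subjects who withdrew from the study will be included in the data listing and summary tables where applicable". Renal response has an explicit rule in SAP 10.7.2, "Subjects who discontinued prior to Week 12 will be counted as non-responders"; the slope has none.

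Protocol 7.10.4 names a random-coefficients model with a slope-by-period test. Protocol 7.10 gives the SAP precedence, and protocol 7.11 bases power on the paired t-test.

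**The concern.** A slope is only as good as its time axis. Following the table literally gives a wrong 12-week slope for every subject sampled on schedule at Day 85. It can also distort the two run-in slopes that decide which baseline is used. It leaves the programmer to decide whether a termination sample is dropped, entered as Day 85 or placed at its own date.

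The t-test also gives every subject's slope equal weight, whatever it rests on. Two programmers could fit whatever points exist or require all listed points, and reach different primary results. With about 20 subjects at most, and treated dropouts not replaced (protocol 4.1), one very imprecise slope can matter. The study is open-label, so a choice made late would be made with results in view.

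**Working it through.** **1. The plan's power figure.** Inputs (SAP 10.1, protocol 7.11): difference 4.6, 4-week slope SD 4.77, about 80% power at n=15 and 90% at n=20. Alpha, sidedness and the SD of the within-subject difference are not stated. With uncorrelated slopes of equal SD, the SD of the difference is 4.77 × √2 = 6.75. An exact paired-t calculation then gives 80.7% and 90.2% at one-sided 5%, or 69.0% and 82.4% at two-sided 5%. So the figure can be reproduced, but only on assumptions of this kind. Step 5 starts from 90% at n=20, two-sided 5%: standardized effect 0.7645, i.e. an SD of the difference of 4.6/0.7645 = 6.02.

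**2. Day 85.** If PCR follows a line in true time t and is regressed on coded time c, then fitted slope / true slope = Σ(c − c̄)t / Σ(c − c̄)². With t ending at 84 and c at 85:
- numerator: 11305 − (190 × 189)/6 = 5320
- denominator: 5373.3
- ratio: 0.990, a 1% understatement.

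**3. Day -35 off by 7 days, coded -35.**
- First 4 weeks: the coded span is 28 days and the true span 35 or 21. Ratios: 35/28 = 1.25 and 21/28 = 0.75.
- Last 4 weeks (-35, -5, 0): the Day -35 point lies 21.67 days from the mean and the sum of squares is 716.7. Change: 21.67 × 7 / 716.7 = 0.21.
- 8 weeks (-63, -35, -5, 0): distance 9.25, sum of squares 2566.75. Change: 9.25 × 7 / 2566.75 = 0.025.

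The first two errors run in opposite directions. With a visit 7 days late, a constant non-zero slope looks 1.25/0.79 ≈ 1.6 times steeper in the first half, which is what triggers the baseline switch.

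**4. Early Termination sample.** Termination at time 20 after samples at 0, 7 and 14, coded 85:
- numerator: 1945 − (106 × 41)/4 = 858.5
- denominator: 7470 − 106²/4 = 4661
- ratio: 0.18.

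The same calculation gives 0.44 at time 40 (after 28) and 0.75 at time 60 (after 56). If the sample is omitted instead, the time-20 leaver's sum of squares falls from 224.75 to 98, so the slope's sampling variance is 2.3 times larger.

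**5. Short series (secondary).** Assume independent equal-variance errors, with Day 1 shared by both slopes. The sampling variance of (treatment slope − 8-week run-in slope), in units of error variance, is:
- full 12-week series: 0.000699
- full 4-week series: 0.003295
- only times 0 and 7: 0.04407.

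The variance ratio R of a Day-8-only subject to a full subject is 63.0 (12-week) or 13.4 (4-week). If true slope variance equals a full subject's sampling variance, the ratio becomes (R + 1)/2 = 32.0 or 7.2. With one such subject in 20, the SE multiplier is √((19 + R)/20). Power is from 400,000 simulated paired t-tests.

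| Contrast with 8-week run-in | Variance assumption | R | SE × | Power |
|---|---|---|---|---|
| 12-week | noise only | 63.0 | 2.02 | 56% |
| 12-week | equal variances | 32.0 | 1.60 | 65% |
| 4-week | noise only | 13.4 | 1.27 | 76% |
| 4-week | equal variances | 7.2 | 1.14 | 82% |

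For a later last sample (12-week, noise only), power is 73% at Day 15 (R 17.2), 85% at Day 29 (R 4.7) and 89% at Day 57 (R 1.6). With no true effect and one Day-8-only subject (12-week, noise only), the test rejects in about 2.8% of trials.

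**The case against.** **Timing.** The footnote can be read as actual study day minus one, which would time a termination sample correctly. Protocol 6.10 heads the Day 85 visit jointly with Early Termination, which points the other way, towards entry as Day 85. So the defect is ambiguity, not a flat absence of any time. It stands because the two readings give very different slopes. The 85/84 slip is small beside the 2-day window on Day 85 itself. The Day -35 figures are proportional errors at the edge of the window; if run-in PCR is flat, the absolute error is small.

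**Short series.** A Day-8-only series should be uncommon. Subjects who exit treatment or are rescued stay in follow-up (protocol 3 and 4.4), and a termination sample is requested. By-subject listings and plots would show an extreme slope. All this stands, and it is why the point is secondary.

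**Stronger readings the documents do not support.** A reader might infer:
- Inflated false positives. The null rejection rate falls below 5%; the harm is lost power and instability.
- That the t-test is unauthorized. Protocol 7.10 and 7.11 allow it. The entry of no changes in SAP 11 is only a missing declaration.
- That the per-protocol repeat gives no protection. Minor deviations include "scheduled assessments omitted or performed in improper sequence", "Subjects with major protocol deviations affecting efficacy evaluation will be excluded from the pP population", and for compliance "The total number of capsules prescribed is calculated as 6 capsules/day x number of days in the duration". But SAP 8 also requires per-protocol subjects to have complied with study drug administration, which may remove someone who stops in week 2. The point is unclear either way.
- That the SDs in protocol 7.11 fix the noise share. That needs equal true-slope variance over 4 and 12 weeks, which mean slopes of -4.62 and -1.32 make doubtful.

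**Conclusion.** The concern holds for the time values. As written, they give a wrong 12-week slope (by 1% on a straight line), allow errors of up to 25% and 21% in the two slopes behind the baseline switch, and leave termination samples open to being lost or badly mistimed. These results need only a linear PCR course and the stated visit windows.

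The missing minimum-data rule is a real gap of lesser weight. The 56% is an extreme: nearly pure noise, loss in the second week and no usable termination sample. It is not an expected loss. The documents give no within-subject PCR variance and no dropout rate, so the powers in step 5 are assumed ranges. It would also go too far to conclude that short series must be excluded from the primary test: early leavers may be treatment failures, and removing them risks selection bias.

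**What to change.** In SAP 10.7.1:
- Compute every slope at the actual sample day relative to first dose, with Day 1 as 0. SAP 10.2.11 already lists study day by date.
- Include Early Termination samples at their actual day.
- Use 84, not 85, wherever nominal times remain.
- Keep the paired t-test on all mITT slopes as primary. Alongside it, report the protocol 7.10.4 random-coefficients slope-by-period model on all mITT PCR values; it down-weights short series without losing subjects.
- Put any minimum-span restriction, for example PCR through Day 29, in a pre-specified sensitivity analysis that lists the subjects left out.
- Record in SAP 11 that the primary test differs from protocol 7.10.4.

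The cost is a few sentences and a little more programming. The primary test loses no subject. In the sensitivity analysis, leaving out one subject lowers power from 90% to about 88% (n=19) on the step 5 basis, and a Day 29 cutoff still lets a 4-week slope count as a 12-week one.
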